### **2.4.9 Analyses of pharmacodynamic variables**

Serum concentrations of IL-6, sIL-6R $\alpha$  and hs-CRP will be summarized using descriptive statistics (including number, arithmetic and geometric means, SD, SEM, CV (%), minimum, median and maximum) by dose regimen cohort and weight group for each visit.

[Redacted line]

[Redacted line]

[Redacted line]

[Redacted line]

[Redacted line]

[Redacted line]

[Appendix C](#) provides mock-up tables to illustrate how the safety events and efficacy endpoints will be summarized before and after dose adjustment in the clinical study reports.

## 2.5 DATA HANDLING CONVENTIONS

### 2.5.1 General conventions

The following formulas will be used for computation of parameters.

#### *Demographic formulas:*

Age at baseline is calculated as follows:

$$\text{Age} = (\text{informed consent date} - \text{birth date})/365.25$$

BMI is calculated as follows:

$$\text{BMI} = \text{Weight in kg}/(\text{height}^2 \text{ in meters}).$$

#### *Renal function formulas:*

Creatinine clearance (CLcr) values will be derived using the equation of Schwartz

- female patients 1-18 years of age and male patients < 13 years of age

$$\text{CLcr (mL/min/1.73m}^2) = (\text{height (cm)} * 0.55)/\text{creatinine (mg/dL)}$$

- male patients  $\geq$  13 years of age

$$\text{CLcr (mL/min/1.73m}^2) = (\text{height (cm)} * 0.7)/\text{creatinine (mg/dL)}$$

For patients grow to >18 years old, the equation of Modification of Diet in Renal Disease (MDRD) will be used (non-Black will be assumed if Race is missing):

- $\text{CLcr (mL/min/1.73m}^2) = 175 * \text{creatinine (mg/dL)}^{-1.154} * \text{Age}^{-0.203} * 1.212 \text{ (if Black)} * 0.742 \text{ (if Female)}$

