- o. Hematology (blood should be drawn PRIOR TO drug administration): Hemoglobin, hematocrit, red blood cell (RBC) count, and morphology (if RBC count is abnormal), white blood cell (WBC) differential (neutrophils, lymphocytes, monocytes, eosinophils, basophils), platelet count, absolute neutrophil count (ANC). An additional hematology test must be performed at Visit 6 (Day 12±1 day) for Dose Regimens 1 and 2 Cohorts in order to get the results before the second dose of sarilumab administration (Visit 7: Week 2, Day 15) or prior to or at Visit 5 (Day 8) for Dose Regimen 3 Cohort (not before Visit 4 [Day 5]) in order to get the results before second dose of sarilumab administration. For patients enrolled in the dose-finding and second portions, the additional hematology test can be done at the central laboratory or at the local laboratory to confirm the neutrophil count and platelet count before the second dose of sarilumab administration. For patients enrolled in the third portion without on-site Visit 6, the additional hematology test will be done at the local laboratory before the second dose of sarilumab administration, but no earlier than Day 12. If local laboratory is used, a central laboratory sample for hematology should still be drawn pre-IMP administration at Visit 7 (Day 15, Week 2) as scheduled for Dose Regimens 1 and 2 Cohorts and Visit 5 (Day 8) for Dose Regimen 3 Cohort. For all patients, the Visit 2 (Day 1) and additional hematology laboratory assessment must be reviewed before the administration of the second dose of sarilumab at Visit 5 (Day 8) for Dose Regimen 3 Cohort patients or at Visit 7 (Week 2, Day 15) for Dose Regimens 1 and 2 Cohort patients.
- p. Chemistry (blood should be drawn BEFORE drug administration): Whole chemistry will be performed at the Screening visit, Baseline Visit 2 (Day1, Week 0) and Visit 12 (Week 12) or EOT only: sodium, potassium, chloride, bicarbonate, blood urea nitrogen, creatinine, and creatinine clearance, glomerular filtration rate (using the modified Schwartz formula), calcium, phosphate, total protein, albumin, alanine aminotransferase (ALT), aspartate aminotransferase (AST), alkaline phosphatase (ALP), total bilirubin, conjugated bilirubin, and unconjugated bilirubin. At all other visits: only ALT, AST, ALP, total bilirubin, conjugated bilirubin, unconjugated bilirubin, and albumin will be tested.

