### 2.1.4.4 Laboratory safety variables

Clinical laboratory data consists of blood analysis, including hematology and clinical chemistry, and urinalysis. Clinical laboratory values will be converted to standard international units; international units will be used in all listings and tables. In addition, the lipid parameters will also be summarized in US units.

Schedule of blood samples for clinical laboratories can be found in Section 1.2 Study Flow Charts of the protocols [REDACTED]

The laboratory parameters will be classified as follows:

- Hematology
  - **Red blood cells and platelets:** hemoglobin, hematocrit, red blood cell (RBC) count and morphology (if RBC count is abnormal), platelet count
  - **White blood cells:** white blood cell (WBC) count, differential (neutrophils, lymphocytes, monocytes, eosinophils, basophils), absolute neutrophil count (ANC)
- Clinical chemistry
  - **Metabolism:** total protein, albumin
  - **Fasting lipids:** triglycerides (TG), total cholesterol, high density lipoprotein (HDL) cholesterol, low density lipoprotein (LDL) cholesterol
  - **Electrolytes:** sodium, potassium, chloride, bicarbonate, calcium, phosphate
  - **Renal function:** blood urea nitrogen (BUN), creatinine, creatinine clearance (using the equation of Schwartz for patients  $\leq 18$  years old and the equation of MDRD when patients grow to  $>18$  years old)
  - **Liver function:** alanine aminotransferase (ALT) (SGPT), aspartate aminotransferase (AST) (SGOT), alkaline phosphatase (ALP), total, conjugated, and unconjugated bilirubin, [REDACTED]

[REDACTED]

Note: Whole chemistry at baseline and week 12 (or EOT) only. At all other visits: albumin, [REDACTED] ALT, AST, ALP, and total, conjugated, and unconjugated bilirubin only.

- **Glycosylated Hemoglobin HbA1C** (screening only): levels will be measured based on the patient's medical history and investigator's judgment
- **hs-CRP and ESR**
- **Pregnancy test:** for females who have commenced menstruating, a serum test is mandatory at screening and urine tests prior to IMP exposure at other indicated visits and EOT
- **Optional: Epstein Barr Virus (EBV), Hepatitis screen, HIV** (screening only): EBV titer including IgG and IgM, hepatitis B surface antigen (HBs-Ag), hepatitis B surface antibody (HBs-Ab), hepatitis B core antibody (HBc-Ab), and hepatitis C antibody (HCV-Ab)
- **Rheumatoid Factor** (baseline only for pcJIA)

Urine samples for urinalysis will be collected at screening only:

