	28 days/1 month to 23 months old (Infants)	< 24 per minutes > 40 per minutes	
	24 months/2 years to <6 years old (Children)	< 22 per minutes > 34 per minutes	
	6 to <12 years old (Children)	< 18 per minutes > 30 per minutes	
	12 to 16/18 years old (Adolescents)	< 12 per minutes > 20 per minutes	
SaO2	All age ranges	≤95 %	
Weight	All ranges	≥5 % weight loss from baseline	Based on identification of trends in the child's growth with a series of visits WHO Multicentre Reference

**CRITERIA for POTENTIALLY CLINICALLY SIGNIFICANT ABNORMALITIES  
For Studies in Children**

Parameter	Age range	PCSA	Comments
			Study Group, 2006; Center for Disease Control. Growth chart 2007
Clinical Chemistry			Ref Molleston JP et al. JPGN 2011; Moritz et al., Pediatrics 1999; Moritz et al., Pediatr Nephrol 2005 ; Sedlacek et al., Seminars in Dialysis 2006) Gong G et al. Clinical Biochemistry 2009; Masilamani et al. Arch Dis Children 2012; Mulberg AE et al. Pediatric Drug Development Concepts and applications. John Wiley & sons, Inc. 2009
ALT/SGPT	All age ranges	$\geq 3$ ULN By distribution analysis: $\geq 3$ ULN $\geq 5$ ULN $\geq 10$ ULN $\geq 20$ ULN	Based on normal ranges: 6 to 50 U/L (0-5 days), 5 to 45 U/L (1-19 years)
AST/SGOT	All age ranges	$\geq 3$ ULN By distribution analysis: $\geq 3$ ULN $\geq 5$ ULN $\geq 10$ ULN $\geq 20$ ULN	Based on normal ranges: 35 to 140 U/L (0-5 days), 15 to 55 U/L (1-9 years), 5 to 45 U/L (10-19 years)
Alkaline Phosphatase	All age ranges	$\geq 1.5$ ULN	Based on normal ranges: 145 to 420 U/L (1-9 years), 130 to 560 U/L (10-11 years), 200 to 495 U/L (Boys 12-13 years), 105 to 420 U/L (Girls 12-13 years), 130 to 525 U/L (Boys 14-15 years), 70 to 130 U/L (Girls 14-15 years), 65 to 260 U/L (Boys 16-19 years), 50 to 130 U/L (Girls 16-19 years)
Total Bilirubin	All age ranges	$\geq 1.3$ ULN	CF = mg x 1.7 = $\mu$ mol Based on normal ranges: <6 mg/dL (Term 0-1 day), <8 mg/dL (Term 1-2 days), <12 mg/dL (Term 3-5 days), <1

**CRITERIA for POTENTIALLY CLINICALLY SIGNIFICANT ABNORMALITIES  
For Studies in Children**

Parameter	Age range	PCSA	Comments
			mg/dL (Term >5 days)
Conjugated Bilirubin	All age ranges	>35% Total Bilirubin and TBILI ≥ 1.3 ULN	CF = mg x 1.7 = μmol Based on normal range: 0 to 0.4 mg/dL
ALT and Total Bilirubin	All age ranges	ALT ≥ 3 ULN and Total Bilirubin ≥ 2 ULN	
CPK	All age ranges	≥ 3 ULN	
Creatinine	Birth/0 to <6 years old (Neonates, Infants, Children)	>53 μmol/L or 0.6 mg/dL	CF = mg x 8.8 = μmol

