	6 years to <12 years old (Children)	≥ 90 μmol/L or 1.1 mg/dL	Based on normal ranges: ≤ 0.6 mg/dL (0-1 year), 0.5 to 1.5 mg/dL (1 to 16/18 years)
	12 years to 16/18 years old (Adolescents)	≥ 132 μmol/L or 1.5 mg/dL	
Creatinine Clearance	All age ranges	50 % of normal < 60 ml/min/1.73m  (After 1 year old)	Based on GFR Bedside Schwartz Formula  Based on normal ranges: 20 to 50 (<8 days), 25 to 80 (8 days to 1 month), 30 to 90 (1-6 months), 40 to 115 (6-12 months), 60 to 190 (12-23 months), 90 to 165 (2-12 years), 80-120 (After 12 years)
Uric Acid	All age ranges	≤ 2.0 mg/dL or 119 μmol/L ≥ 8.0 mg/dL or 476 μmol/L	CF = mg x 5.95 = μmol Based on normal ranges: 2.4 to 6.4 mg/dL
Blood Urea Nitrogen (BUN)	Birth/0 to 27 days old (Neonates)	≥ 4.3 mmol/L or 12 mg/dl	CF = g x 16.66 = mmol
	28 days/1 month to 16/18 years old (Infants, Children, Adolescents)	≥ 6.4 mmol/L or 18 mg/dl	Based on normal ranges: 3 to 12 mg/dL (NN); 5 to 18 mg/dL (other classes of age)
Chloride	All age ranges	≤ 80 mmol/L or 80 mEq/L ≥ 115 mmol/L or 115 mEq/L	CF = 1  Based on normal range: 98 to 106
Sodium	All age ranges	≤ 129 mmol/L or 129 mEq/L ≥ 150 mmol/L or 150 mEq/L	CF = 1

**CRITERIA for POTENTIALLY CLINICALLY SIGNIFICANT ABNORMALITIES  
For Studies in Children**

Parameter	Age range	PCSA	Comments
			Based on normal range : 134 to 146
Potassium	Birth/0 to 27 days old (Neonates)	≤3.0 mmol/L or 3.0 mEq/L ≥7.0 mmol/L or 7.0 mEq/L	CF = 1 Based on normal ranges: 3.0 to 7.0 (NN); 3.5 to 6.0 (Infants); 3.5 to 5.0 (>Infants)
	28 days/1 month to 23 months old (Infants)	≤3.5 mmol/L or 3.5 mEq/L ≥6.0 mmol/L or 6.0 mEq/L	
	24 months/2 years to 16/18 years old (Children, Adolescents)	≤3.5 mmol/L or 3.5 mEq/L ≥5.5 mmol/L or 5.5 mEq/L	
Bicarbonate	All age ranges	≤16 mmol/L or 16 mEq/L ≥30 mmol/L or 30 mEq/L	CF = 1 Based on normal range: 18 to 26
Calcium total	All age ranges	≤2.0 mmol/L or 8.0 mg/dL ≥2.9 mmol/L or 11.6 mg/dL	CF = mg x 0.025 = mmol Based on normal range: 8.4 to 10.9 mg/dL
Calcium ionized	All age ranges	≤1.0 mmol/L or 4.0 mg/dL ≥1.4 mmol/L or 5.6 mg/dL	CF = mg x 0.025 = mmol Based on normal range: 4.0 to 5.1 mg/dL

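### SAP 2.5.1 derives creatinine clearance with Schwartz coefficients 0.55/0.7, while Appendix A attributes the clearance PCSA limit to the Bedside Schwartz formula; the 0.55/0.7 rule also puts a 27% step into a boy's series at age 13

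*SAP*

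**What the plan says.** SAP 2.5.1 (renal function formulas) opens with "Creatinine clearance (CLcr) values will be derived using the equation of Schwartz". It gives height (cm) × 0.55 / creatinine (mg/dL) for females aged 1-18 and males under 13, and height × 0.7 / creatinine for males of 13 and over. MDRD applies above 18. SAP 2.1.4.4 repeats this under renal function: "creatinine clearance (using the equation of Schwartz for patients" up to 18, then MDRD. That list holds BUN, creatinine and creatinine clearance, and no separate GFR.

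In SAP Appendix A the creatinine clearance criterion reads "50 % of normal < 60 ml/min/1.73m 2 (After 1 year old", and its comment is "Based on GFR Bedside Schwartz Formula". No coefficient is given. SAP 2.4.5 (general common rules) and 2.4.5.3 count PCSAs directly from Appendix A.

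Protocol 1.2.1 (footnote p) and 9.3.4 list creatinine clearance and, as a further item, "glomerular filtration rate (using the modified Schwartz formula". No coefficient is given there either, and no section reconciles the three descriptions.

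**The concern.** A threshold means something only on the scale it was set for. Here the computed clearance comes from one named version of the Schwartz equation and the limit is attributed to another. If the coefficients differ, the count of patients below 60 is not the count that the limit was meant to give.

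The 0.55/0.7 rule also breaks the continuity of a boy's own series at 13. Change from baseline in every laboratory variable is a planned output (SAP 2.4.5.3), so the break reaches that table. The outputs at stake are the renal PCSA incidence and the clearance change from baseline, both safety tabulations in children.

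**Working it through.** The documents state no figure for the size of the mismatch, so there is none to reproduce.

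**1. From the documents alone: the step at 13.** Both SAP formulas have the form k × height / creatinine. With height and creatinine unchanged, the ratio at the 13th birthday is 0.7/0.55 = 1.273, a rise of 27%. A true fall of 1 − 0.55/0.7 = 21.4% would show as no change. This assumes that age at the assessment selects the formula. SAP 2.5.1 does not say so outright, but it moves patients to MDRD as they pass 18, which implies it. End-of-treatment chemistry is at Week 156 in the first two portions (about 3 years) and Week 96 in the third (about 1.8 years). Boys aged about 10-12, or 11-12, at entry can therefore cross the boundary.

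**2. From the documents alone: the clearance limit against the creatinine limits.** Appendix A has a separate creatinine PCSA: >0.6 mg/dL under 6 years, ≥1.1 at 6 to <12, ≥1.5 from 12. The SAP clearance equals 60 at creatinine k × height / 60. In boys of 13 and over, this exceeds 1.5 mg/dL once height passes 1.5 × 60 / 0.7 = 129 cm. Above that height the creatinine flag always comes first and the clearance criterion adds nothing. The corresponding heights are 120 cm at 6 to <12 (1.1 × 60 / 0.55) and 65 cm under 6 (0.6 × 60 / 0.55).

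**3. Size against the named formula (assumed coefficient kB).** Excess = k/kB − 1. The bedside value at which the SAP result reaches 60 is 60 × kB/k.

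| Assumed kB | Excess, 0.55 | Excess, 0.7 | Bedside value at SAP 60 (0.55) | Bedside value at SAP 60 (0.7) |
|---|---|---|---|---|
| 0.35 | 57.1% | 100.0% | 38.2 | 30.0 |
| 0.40 | 37.5% | 75.0% | 43.6 | 34.3 |
| 0.413 | 33.2% | 69.5% | 45.1 | 35.4 |
| 0.45 | 22.2% | 55.6% | 49.1 | 38.6 |
| 0.55 | 0.0% | 27.3% | 60.0 | 47.1 |

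**4. What neither PCSA catches, at kB = 0.413.** The heights are assumptions. The creatinine limit corresponds to a bedside value of 0.413 × height / limit.

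| Group | Heights (cm) | Bedside value at creatinine limit | Bedside value at SAP 60 | Missed by both |
|---|---|---|---|---|
| Under 6 | 85-115 | 58.5-79.2 | 45.1 | at most 58.5-60 |
| 6 to <12 | 115-150 | 43.2-56.3 | 45.1 | 45.1-60, narrowing to 56.3-60 |
| Boys aged 12 | 145-160 | 39.9-44.1 | 45.1 | 45.1-60 |
| Girls 12-17 | 150-170 | 41.3-46.8 | 45.1 | 45.1-60, narrowing to 46.8-60 |
| Boys 13 and over | 155-180 | 42.7-49.6 | 35.4 | 42.7-60, narrowing to 49.6-60 |

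The widest band is about 43-60, and there is almost none under 6. Example: a 165 cm boy of 13 or over reaches an SAP clearance of 60 at creatinine 165 × 0.7 / 60 = 1.93 mg/dL, against 165 × 0.413 / 60 = 1.14 on the assumed bedside scale. The creatinine PCSA flags him at 1.5, which is a bedside value of 0.413 × 165 / 1.5 = 45. His tabulated clearance is then 0.7 × 165 / 1.5 = 77.

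**The case against.** **The coefficient is external.** This stands. A reader might infer that the SAP overstates clearance by 33-69% as a matter of fact. The documents do not support that: the figure needs a bedside coefficient near 0.413, which they nowhere give. At 0.55 the discrepancy for girls and younger boys disappears. The mismatch of named formulas and the step at 13 need no outside number.

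**The protocol does not contradict the SAP formula.** This also stands. The modified Schwartz formula is tied to GFR, listed separately from creatinine clearance, and no section equates modified with bedside. What remains is that the SAP renal list omits the protocol's GFR.

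**Appendix A is a generic paediatric table, and the comment may only record where the limit came from.** This is possible, since the table also covers neonates and ECG parameters. But a limit taken from one formula still needs justification when it is applied to another, and the SAP applies Appendix A directly. The entry about 50% of normal in the same row is unclear as well.

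**Other outputs catch much of the gap.** This is largely right. Besides the creatinine PCSA, SAP 2.4.5.3 plans shift tables for values below the normal range and listings that flag out-of-range values. If the ranges in the Appendix A comments were used (90-165 at 2-12 years, 80-120 after), a bedside value below 60 becomes an SAP value below 79.9 in the 0.55 group (at 0.413), which reads as low. In older boys this holds only below 80 × 0.413 / 0.7 = 47. Serum creatinine also has its own change-from-baseline summary.

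**Few values are affected.** SAP 2.1.4.4 limits whole chemistry to baseline and Week 12 or end of treatment. Protocol 10.1.9.2.1 adds complete profiles only for patients who switch to the selected dose. This limits the reach of the problem but does not remove it.

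**Conclusion.** The inconsistency is real and specific: SAP 2.5.1 and Appendix A attribute the clearance value and its PCSA limit to different formulas. The step of 27% at 13, able to mask a 21% fall in change from baseline, follows from the SAP's own coefficients provided that age at the assessment selects the formula.

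The size of the threshold mismatch is conditional. For a bedside coefficient of 0.40-0.45, SAP values are 22-38% or 56-75% higher, and the clearance criterion is met only below bedside values of about 44-49 or 34-39. At 0.413 and the assumed heights, the band missed by both PCSAs is roughly 43-60, mainly from age 6.

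Two stronger readings are tempting. One is that moderate renal decline goes unflagged. The creatinine PCSA and the out-of-range outputs show that this is too broad. The other is that 60 is an alert limit on which a child's care depends. It is not: PCSAs feed tables and listings, and the protocol handles renal abnormalities through the serum creatinine guidance in its Appendix G. This is a point about safety tabulation.

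**What to change.** For patients up to 18, derive the clearance value used for the PCSA and for change from baseline with the formula on which the limit is based (Bedside Schwartz), and state its coefficient. Word it identically in SAP 2.1.4.4, 2.5.1 and Appendix A. Say how the entry about 50% of normal is to be applied.

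If 0.55/0.7 is kept for descriptive summaries, use the same coefficient at baseline and follow-up within a patient for change from baseline. Where height is not measured with the chemistry, use the most recent height. For example, Protocol 10.1.9.2.1 takes height at Visit 101 but also lists complete chemistry at Visits 102, 103, 105 and 106.

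The cost is SAP wording and one derivation, with no new data. If the coefficient is below the SAP's, reported clearances will be somewhat lower and a few more patients may be flagged.

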- j. Chemistry (blood should be drawn BEFORE drug administration): ALT, AST, ALP, total bilirubin, conjugated bilirubin, unconjugated bilirubin, and albumin will be tested. Complete chemistry (refer to [Section 9.3.4](#)) should be done at Visit 27 EOT (Week 156). If a patient discontinues prematurely before Week 96, the test must be performed by the central laboratory at EOT.
- k. Lipids (blood should be drawn BEFORE drug administration): Triglycerides (TG), total cholesterol, high density lipoprotein (HDL) cholesterol, low density lipoprotein (LDL) cholesterol. Patients are required to fast at least 8 hours before the test. At EOT, the test will be performed only for patient who discontinues prematurely before Week 96 and must be performed by the central laboratory.
- l. At EOT, the ANA/anti-dsDNA antibody test will be performed only for patient who discontinues prematurely before Week 96 and must be performed by the central laboratory.
- m. For females who have commenced menstruating, urine pregnancy tests should be performed prior to exposure to the IMP at each scheduled visit and at the EOT. The urine pregnancy test could be performed locally.
- n. Blood samples will be collected PRIOR TO IMP administration on the dosing days during the treatment period. If an SAE occurs in a patient, blood samples should be collected for determination of sarilumab concentration and anti-drug antibody (ADA) assessment at or near the onset and completion of the occurrence of the event, if possible (see [Section 9.1](#)).

1.2.2.2 Flow chart for patients enrolled in the dose-finding portion who change to the selected dose regimen (during extension phase)

Visit	Visit (up to a total of 144 weeks of sarilumab exposure from V12)														Post-treatment follow-up (6 weeks)							
	V101	V102	V103	V104	V105	V106	V107	V108	V109	V110	V111	V112	V113	V114		V115	V116	V117	V118	V119	V27 ^a	V28 ^b
Day at this dose	D 1 (±1 or 3)	D 15 (±1 or 3)	D 29 (±1 or 3)	D 43 (±1 or 3)	D 57 (±1 or 3)	D 85 (±1 or 3)	D 113 (±1 or 3)	D 141 (±1 or 3)	D 169 (±1 or 3)	D 225 (±1 or 3)	D 281 (±1 or 3)	D 337 (±1 or 3)	D 421 (±1 or 3)	D 505 (±1 or 3)	D 589 (±1 or 3)	D 673 (±1 or 3)	D 757 (±1 or 3)	D 841 (±1 or 3)	D 925 (±1 or 3)	EOT	EOS: (EOT +6 Weeks)	
Week at this dose	Wk 0	Wk 2	Wk 4	Wk 6	Wk 8	Wk 12	Wk 16	Wk 20	Wk 24	Wk 32	Wk 40	Wk 48	Wk 60	Wk 72	Wk 84	Wk 96	Wk 108	Wk 120	Wk 132	Check Table 1 for the weeks between patient's last on-treatment visit and EOT	(EOT +6 Weeks)	

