- g Investigational medicinal product (IMP) to be administered once every other week (q2w). Patients should be monitored for at least 30 minutes after IMP administration for any signs or symptoms of a hypersensitivity reaction. The last IMP injection will occur at Week 94; then patients will have EOT assessment at the Visit 27 (Week 96 for third portion). There will be no IMP injection at the Visit 27.

- h* Height will be measured using stadiometer at sites during the study.
- i* Juvenile Idiopathic Arthritis American College of Rheumatology (JIA ACR) core set includes: global assessment of the severity of disease by the physician, global assessment of overall well-being by the patient or parent, number of joints with active arthritis (defined as swelling within the joint not due to deformity OR limitation of motion and with either pain, tenderness, or both), number of joints with limitation of motion, Childhood Health Assessment Questionnaire (CHAQ), and hs-CRP (2, 3, 4). If a patient discontinues prematurely before Week 48, hs-CRP must be performed by the central laboratory at EOT.
- j* Juvenile Arthritis Disease Activity Score scoring is explained in [Section 9.4.2](#).
- k* Hematology (blood should be drawn PRIOR TO drug administration): Hemoglobin, hematocrit, red blood cell (RBC) count and morphology (if RBC count is abnormal), white blood cell (WBC) differential (neutrophils, lymphocytes, monocytes, eosinophils, basophils), platelet count, absolute neutrophil count (ANC). If a patient discontinues prematurely before Week 48, the test must be performed by the central laboratory at EOT.
- l* Chemistry (blood should be drawn BEFORE drug administration): ALT, AST, ALP, total bilirubin, conjugated bilirubin, unconjugated bilirubin, and albumin will be tested. Complete chemistry (refer to [Section 9.3.4](#)) should be done at Visit 27 EOT (Week 96 for third portion). If a patient discontinues prematurely before Week 48, the test must be performed by the central laboratory at EOT.
- m* Lipids (blood should be drawn BEFORE drug administration): Triglycerides (TG), total cholesterol, high density lipoprotein (HDL) cholesterol, low density lipoprotein (LDL) cholesterol. Patients are required to fast at least 8 hours before the test. At EOT, the test will be performed only for patient who discontinues prematurely before Week 48 and must be performed by the central laboratory.

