##### *General common rules*

All safety analyses will be performed on the safety population as defined in [Section 2.3.2](#), unless otherwise specified, using the following common rules:

- The baseline value is defined as the last available value prior to the first dose of the study medication.
- The potentially clinically significant abnormality (PCSA) values are defined as abnormal values considered medically important by the Sponsor according to predefined criteria/thresholds based on literature review and defined by the Sponsor for clinical laboratory tests and vital signs ([Appendix A](#)).

- PCSA criteria will determine which patients had at least 1 PCSA during the TEAE period, taking into account all evaluations performed during the TEAE period, including nonscheduled or repeated evaluations. The number of all such patients will be the numerator for the on-treatment PCSA percentage.
- The treatment-emergent PCSA denominator by group for a given parameter will be based on the number of patients assessed for that given parameter in the TEAE period by dose regimen cohort on the safety population.
- For quantitative safety parameters based on laboratory measurements, descriptive statistics will be used to summarize result and change from baseline values by visit and dose regimen cohort. Summaries will include the endpoint value. The endpoint value is commonly defined as the value collected at the same day/time of the last dose of IMP. If this value is missing, this endpoint value will be the closest one prior to the last dose intake.
- Analyses of the safety variables will be essentially descriptive and no systematic between-group testing is planned.

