#### **2.4.5.3 Analyses of laboratory variables**

The summary statistics (including number, mean, median, SD, minimum and maximum) of all laboratory variables (laboratory values and changes from baseline) will be calculated for each visit or study assessment (baseline, each post-baseline time point, endpoint) by dose regimen cohort. This section will be organized by biological function as specified in [Section 2.1.4.4](#).

In addition, for all laboratory parameters, the mean value and mean change from baseline at each scheduled visit will be plotted by dose regimen cohort.

The incidence of PCSAs ([Appendix A](#)) at any time during the TEAE period will be summarized by biological function and dose regimen cohort whatever the baseline level and/or according to the following baseline status categories:

- Normal/missing
- Abnormal according to PCSA criterion or criteria.

For lipids, the NCEP APTIII classification will be used for the baseline.

The incidence of PCSAs at any time during the post-study period will be summarized by the actual dose regimen cohort received in the 12-week core treatment period.

The incidence of abnormal laboratory values at any time during the TEAE period will be summarized in shift tables by biological function and dose regimen cohort whatever the baseline level and/or according to the following baseline status categories:

- Normal/Missing
- Abnormal high according to the normal range
- Abnormal low according to the normal range

Listings will be provided with flags indicating the out of range values as well as the PCSA values.

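### Creatinine clearance changes from Schwartz to MDRD after age 18, but no visible rule says how to compute change from baseline or the baseline-status PCSA split across the change

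*SAP*

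**What the plan says.** SAP 2.5.1 (renal function formulas) gives CLcr in mL/min/1.73 m² as 0.55 × height / creatinine for females aged 1-18 and males under 13, and 0.7 × height / creatinine for males of 13 or more. After 18 the equation changes: "For patients grow to >18 years old, the equation of Modification of Diet in Renal Disease (MDRD) will be used". MDRD carries a factor of 0.742 for females and 1.212 for Black patients. SAP 2.1.4.4 repeats the rule: Schwartz up to 18, "and the equation of MDRD when patients grow to" an age above 18.

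SAP 2.4.5.3 says that summary statistics "of all laboratory variables (laboratory values and changes from baseline) will be calculated for each visit or study assessment", with no exception for CLcr. It tabulates PCSAs by baseline status (normal/missing, or abnormal by the PCSA criterion). SAP 2.4.5, general common rules, states: "PCSA criteria will determine which patients had at least 1 PCSA during the TEAE period". Appendix A sets the CLcr criterion after 1 year of age at below 60 mL/min/1.73 m², whichever equation produced the value.

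Patients must be 17 or younger only at Screening (Protocol 7.1). Complete chemistry, which includes creatinine, is done at baseline, Week 12 and end of treatment (EOT). EOT is Week 156 in the dose-finding and second portions and Week 96 in the third (Protocol 1.2.2 footnotes).

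**The concern.** A change from baseline is interpretable only if both values are on the same scale. A patient who enters at 16 or 17 has a Schwartz baseline and, at EOT, an MDRD value. The difference then mixes any renal change with the difference between two equations, and the table does not separate them.

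The same patient can be counted as normal at baseline and abnormal on treatment although creatinine has not moved. In a study of about 100 treated patients, even one such renal flag would stand out and need explaining.

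**Working it through.** The plan gives no figure for the size of this effect, so none can be reproduced. The check evaluates the two SAP 2.5.1 equations at the same height and creatinine.

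**Inputs**
- Equations and factors: SAP 2.5.1.
- Creatinine 0.5-1.5 mg/dL: the range that Appendix A gives as normal for 1 to 16/18 years.
- CLcr cut-off 60, and adolescent (12 to 16/18 years) creatinine PCSA limit 1.5 mg/dL: Appendix A.
- Heights: assumed, 150-175 cm for females and 160-190 cm for males. The documents give none.
- Age: 18.01 years (just past 18), reading the limit as exact age at the visit.

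**Formulas**
- Schwartz = k × height / Cr, with k = 0.55 (female) or 0.7 (male of 13 or more).
- MDRD = 175 × Cr^-1.154 × age^-0.203 × 0.742 (if female) × 1.212 (if Black).
- Shift due to the equation alone = MDRD / Schwartz − 1.

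**Worked cases, without the 1.212 factor** (18.01^-0.203 = 0.5561)

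| Patient | Schwartz | MDRD | Shift |
|---|---|---|---|
| Female 163 cm, 0.7 mg/dL | 0.55 × 163 / 0.7 = 128.1 | 109.0 | −15% |
| Male 175 cm, 0.8 mg/dL | 0.7 × 175 / 0.8 = 153.1 | 125.9 | −18% |
| Female 163 cm, 1.2 mg/dL | 0.55 × 163 / 1.2 = 74.7 | 175 × 0.8103 × 0.5561 × 0.742 = 58.5 | −22% |

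**Range of MDRD / Schwartz over the assumed heights and creatinine**
- Without 1.212: female 0.705-0.974, male 0.687-0.967, a fall of 3-31%.
- With 1.212: female 0.854-1.180, male 0.833-1.172, so either direction.
- Shorter patients can rise without the factor: male 150 cm, 0.5 mg/dL, 210.0 to 216.5 (+3%).
- At 20.98 years, without the factor: female 0.683-0.944, male 0.666-0.937, a fall of 6-33%.

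**New flags.** A flag is created where Schwartz is at least 60 and MDRD is below 60.
- Female, without the factor: MDRD reaches 60 at 1.174 mg/dL. Schwartz reaches 60 at 0.55 × height / 60, which is 1.375 at 150 cm and 1.494 at 163 cm. The window is therefore 1.17-1.37 and 1.17-1.49 mg/dL respectively, below the 1.5 mg/dL creatinine limit, so that limit would not be met as well.
- Female, with the factor: MDRD reaches 60 at 1.387 mg/dL. There is no window at 150 cm; at 163 cm it is 1.39-1.49.
- Male, without the factor: MDRD reaches 60 at 1.521 mg/dL, so a male newly flagged just past 18 is already above 1.5 mg/dL.

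**Who can be affected.** Converting weeks to years (× 7 / 365.25), Week 156 is 2.99 and Week 96 is 1.84. Patients above 18 − 2.99 = 15.0 years at baseline can pass 18 by Week 156, and those above 16.2 by Week 96. Their number is not given.

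**Adjacent limit in Appendix A.** In the creatinine rows, 132 µmol/L is paired with 1.5 mg/dL (132 / 1.5 = 88) and 53 with 0.6 (53 / 0.6 = 88.3). The 6 to <12 years row pairs 90 µmol/L with 1.1 mg/dL. At 88, 1.1 mg/dL is 96.8 µmol/L and 90 µmol/L is 1.02 mg/dL.

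**The case against.** The strongest reply is that this matters little. Safety analyses are descriptive, without testing. Protocol 10.6.8 says sarilumab is not known to have a clinically significant effect on renal function. Creatinine has its own summaries and PCSA, so an unchanged creatinine beside a falling CLcr would be visible. The flagged example starts at 74.7, already below the 80-120 that Appendix A calls normal after 12 years. Using MDRD in adults is a deliberate choice, stated twice. All of this stands. It limits the consequence and supports keeping MDRD for reported values, but it does not make a Schwartz-to-MDRD difference a valid change score.

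The absence of a rule cannot be called certain. SAP 1.5, 1.6 and 2.4.5.6 are in the contents list but not in the text supplied. The sections where a rule would naturally sit (2.4.5 common rules, 2.4.5.3, 2.5.1) are legible and silent.

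Three stronger readings are tempting and not supported:
- **That the switch always lowers CLcr by 3-31%.** That range needs the assumed heights and omits a factor printed in the same formula; with the factor, or in shorter patients, CLcr can rise.
- **That the PCSA itself is computed across the switch.** The below-60 criterion is an absolute cut with no change term. Only the change score and the baseline-status split span the two equations; a new flag comes from applying one cut-off to both.
- **That the Appendix A comment "Based on GFR Bedside Schwartz Formula" proves the cut-off conflicts with the 2.5.1 coefficients.** The documents give no coefficient for that formula, so no mismatch can be shown from them.

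**Conclusion.** The point holds in limited form. On the visible text, patients who pass 18 between baseline and a later complete-chemistry visit get a change score, and possibly a normal-to-abnormal shift, that partly or wholly reflects the change of equation. At ordinary creatinine the artefact is about 15-18% downward without the 1.212 factor, and its size and direction depend on sex, race factor, height and creatinine. Flags created below the 1.5 mg/dL creatinine limit arise essentially in females.

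The sizes rest on assumed heights, unchanged creatinine and exact age above 18. The reach is one descriptive parameter, mainly at EOT. Dose switchers may be affected sooner: Protocol 10.1.9.2.1 lists complete chemistry at Visits 101, 102, 103, 105 and 106, although the flow-chart footnote in 1.2.2.2 lists the short panel. No efficacy or PK conclusion is touched.

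A reader might also infer that the 13-year coefficient cut in boys should be fixed at baseline age, since age is defined only there. That does not follow: SAP 2.5.1 assigns 0.7 from 13, and holding a growing boy at 0.55 would create an artefact of its own.

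**What to change.** 1. In SAP 2.5.1, with a cross-reference in 2.4.5.3, keep MDRD for reported CLcr values after 18. For change from baseline and for the baseline-status (treatment-emergent) PCSA split, derive both the baseline and the later value with the equation that applied at that patient's baseline. In the listing, mark any CLcr flag that arises only under MDRD. With unchanged height and creatinine, the 163 cm female at 1.2 mg/dL then stays at 74.7 in the comparison, and her 58.5 appears as a marked MDRD value.
2. In Appendix A, reconcile the 6 to <12 years creatinine limit so that its µmol/L and mg/dL figures agree.

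Cost: a few lines of SAP text and derivation code, with no new data. Downside: the change score uses a paediatric equation in patients up to about 21 years; the reported MDRD values cover that.
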